6.1 Recruitment

Healthy free-living individuals will be recruited through community, university campus and hospital based efforts.

6.1.1 Recruitment procedure

Recruitment will be focused on recruiting healthy free-living individuals who have normal blood sugar levels. These subjects will include those recruited by the community and hospital based protocol.

6.1.2 Proposed Recruitment methods

Different recruitment platforms will be used in order to reach our target sample size; the following sources will be used:

- Posters outlining the study initiative will be placed in public areas including hospital waiting rooms and universities, contact information for the research investigator will be available.
- Study information will be circulated internally by email at University College Dublin as well as at its affiliated hospital, St. Vincent's University Hospital.
- Social media websites / advertisements / news stories / trial websites etc. will only contain essential documentation approved by the ethics committee (patient information

sheet, trial contact details etc.). We may set up social media pages such as Twitter / Facebook which will contain basic trial contact details and referral to the website.

Potential participants identified through those methods will be able to make contact with the research investigator and they will receive written information detailing the study and be invited to attend a screening visit. If required, an open advertisement will be placed in national newspaper.

6.2 Inclusion/Exclusion criteria

The inclusion and exclusions criteria for the study are outlined below and in order to participate in the study patients must comply with these criteria.

6.2.1 Inclusion Criteria

- Age: 18-50 years
- Normal fasting glucose
- Stable body weight for at least last three months
- BMI < 30 Kg/m²
- Capacity to consent to participate
- Independently mobile

6.2.2 Exclusion Criteria

Patients who meet any of the following criteria will be excluded:

- Pre-diabetes
- Diabetes
- Obesity
- Smoking
- Substance abuse
- Pregnancy
- Use of medications (except for oral contraceptives)
- Chronic medical or psychiatric illness
- Any significant abnormalities detected on physical examination, electrocardiography, or screening blood tests (measurement of complete blood count, electrolytes, fasting glucose, and liver function).

6.3 Visit and procedures

Table 1: Schedule of Study Visits and Events

Trial Periods	Screening	V1	V2	V3	V4	V5	V6	Premature discontinuation	Follow up/ Premature discontinuation
Timing of visit (weeks)	-1	1	2	3	4	5	6		
Informed Consent	X								
Eligibility Assessment	X								
Record medications and illnesses	X							X	X
Anthropometric Measurements	X							X	X
Blood Samples		X	X	X	X	X	X		
Randomisation		X	X	X	X	X	X		
Visual Analogue Scales		X	X	X	X	X	X		
Adverse events		X	X	X	X	X	X	X	X

6.3.1 Screening Visit

- Informed Consent
- Eligibility Assessment
- Anthropometric Measurements (Weight, height, BMI and waist circumference).

6.3.2 Subsequent study visits

6.3.2.1 Study Visit 1 - 6 (Week 1 - 6)

- Record current and past medications and illnesses
- Randomisation to protein microcapsules or placebo
- Visual Analogue Scales

6.4 Description of procedures and measurements

6.4.1 Participant Information and Consent

In advance of the study, volunteers will have received a copy of the participant information. Any questions and concerns that remain can be discussed with the investigator at the screening visit. If the volunteer meets the inclusion criteria and is satisfied to proceed with recruitment to the study, they will be asked to sign the consent form prior to the initiation of any further elements of the study visit. As part of this process, every participant will be advised of their right to refuse to participate or to withdraw at any time without impediment to their medical care in accordance with Good Clinical Practice guidelines. Withdrawal from the study can be done at any time by contacting the hospital or research team. If a participant chooses to participate, and subsequently withdraws their consent, all blood samples, records or footage in storage will be destroyed and the information stored will be deleted so it cannot be used again.

6.4.2 Medical history

A medical history will be performed at the screening visit to record illnesses, disorders and medications. This information needs to be updated on all follow-up visits.

6.4.3 Vital Signs

Pulse should be recorded at all visits after resting for five minutes in a sitting position. Systolic and diastolic blood pressure will be measured preferably in sitting position at all visits.

6.4.4 Anthropometric measurements

To minimise variability all anthropometric measurements will be taken by the same investigator throughout the study, as is practically feasible. Measurements will be taken between 8 and 10am while the volunteer is in a fasted state. Volunteers will be asked to void before measurements are performed. All measurements should be conducted in the presence of a chaperone

6.4.4.1 Weight measurement

Study participants will have their weight measured on a digital calibrated scale. Volunteers will be weighed in their clothing with their shoes off and in barefeet or socks. Measurements will be recorded to the nearest 0.1Kg.

6.4.4.2 Height measurement

Study participants will have their height measured using a stadiometer. This measurement will be taken in bare feet or socks. Patients will be asked to stand upright with their heels, buttocks and occiput touching the backboard of the stadiometer. The measuring arm of the stadiometer will be brought down to the top of the subjects head. Height is recorded to the nearest 0.1cm.

6.4.4.3 Waist circumference

A non-stretch tape measure will be used to measure waist circumference. The measurement will be taken with the subject in a standing position with the abdomen relaxed, the arms at the sides and the feet together and breathing normally. The measurer faces the subject and places a measuring tape around the subject in a horizontal plane, at the mid-point between the lowest rib and the supra iliac crest. The measurement should be taken at the end of a normal expiration, ensuring the tape is taut around the subject's waist, without compressing the skin. Waist circumference measurements will be taken in duplicate and values will be recorded to the nearest 0.5cm. The mean value of both measurements will be recorded as the waist circumference.

6.4.4.4 Visual analogue Scales

Visual analogue scales will be used to assess subjective feelings of malaise, nausea and symptoms of flushing (Appendix B)

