Methods: Ten healthy volunteers, aged 18 to 65 years will be recruited. Each subject will be studied on six occasions one week apart. Prior to each study day, the subjects will consume an identical meal between 19.00 and 20.00 on the night before and refrain from alcohol and strenuous exercise for the 24 hours before and after each study day.

Subject will arrive to the Clinical Research Centre at St Vincent University Hospital at 08.30 having fasted the night before from 20.00. At 9:00 am a cannula will be inserted into the antecubital vein of the forearms. About 5 mL (1 teaspoon equivalent) will be taken to measure baseline hormone level. Another blood samples will be taken every 30 minutes thereafter. At 12:00, a final blood sample will be withdrawn and the cannula will be removed (total blood samples 7).

They will be asked to answer a questionnaire regarding your feeling of hunger, satiety and if there is any nausea on a linear scale. Then a drink containing 200 grams of macronutrient microcapsules suspension equating to 1087 kcal will be offered.

In a randomized way all subjects will receive a mixed meal containing 200 grams of macronutrient microcapsules suspension equating to 1087 kcal in their successive weekly visits:

- Option 1 High protein mixed meal in capsules that break down in the stomach,
- Option 2 High protein mixed meal in capsules that break down in the distal small bowel,
- Option 3 High fat mixed meal in capsules that break down in the stomach,

- Option 4 High fat mixed meal in capsules that break down in the distal small bowel,
- Option 5 High CHD mixed meal in capsules that break down in the stomach,
- Option 6 High CHD mixed meal in capsules that break down in the distal small bowel.

After 3 hours (i.e. at 12:00) participants will be offered standard *ad libitum* meal to measure their food consumption and another blood sample will be drawn. All subjects will be asked to rate their appetite on a Visual Analogue Scale (VAS) (see appendix B). Upon VAS completion the subjects will be allowed to go home.

Blood sample will be withdrawn from participants at the beginning and at the end of each visit. These samples will be used to quantify gut hormone levels

Conclusion:

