5.3 Primary endpoint

Changes in appetite as measured by visual analogue scale

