5.5.1 Design (10 subjects)

5.5.2 Macronutrient microcapsules

- The microcapsules will be stored in line with manufacturer instructions.
- As the study drug will be blinded to the research investigator
- The Microcapsules will be introduced by the research nurse and labelled with the appropriate code drink A, B, C, D, E or F.
- It will be given at 9:00 am on an empty stomach prior to the meal.

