5.5.3 Study procedures

At the screening visit a doctor or nurse will then perform the following tests and procedures to determine if the subject is eligible for the study:

- Medical history
- Physical examination
- Body measurements including height, weight and waist circumference
- Record of your medications or illnesses
- Urine pregnancy test (if applicable)

Visit 1-6 (1 week apart):

Subjects will be randomised to consume a one the 6 microcapsules in each week. Internet-based randomisation software will be used to allocate microcapsules to each subject at each visit

Eligible subjects will be invited to six consecutive visits in the clinical research centre at St Vincent University Hospital. On each occasion we would request you to have identical meals the night before between 19:00 and 20:00 hours and fast thereafter. Please refrain from alcohol and strenuous exercise for 24 hours before each study visit.

1. Food intake for the 24 h before each study day should be similar.
2. Participants will be asked to consume an identical meal between 19.00 and 20.00 on the night before each study (fish or pasta meal).
3. They will also be asked to be fasted and drink only water from 20.00 the night before the study.

In each visit, participants will be asked to be in the clinical research centre at 8:30. At 9:00 am a cannula will be inserted into the antecubital vein of the forearms. About 5 mL (1 teaspoon equivalent) will be taken to measure baseline hormone level. Another blood samples will be taken every 30 minutes thereafter. At 12:00, a final blood sample will be withdrawn and the cannula will be removed (total blood samples 7). They will be asked to answer a questionnaire regarding your feeling of hunger, satiety and if there is any nausea on a linear scale. Then a drink containing 200 grams of macronutrient microcapsules suspension equating to 1087 kcal will be offered. At 12:00 an *ad libitum* meal will be offered. After the meal they will also be provided with a similar questionnaire to fill in, in order to establish your fullness and satiety level. The total visit time is around five hours and there is a total of approximately 35 ml of blood (less than 2 table spoons) at each visit 1 to 6.

6 Methodology

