Appendix B: VISUAL ANALOGUE SCALE

[figure not shown]
How anxious do you feel?

[figure not shown]
How stressed do you feel?

How sick/Nauseated do you feel?

How dizzy do you feel?

How flushed do you feel?

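### The primary appetite endpoint names no item, direction or rating times, and the only ratings with a described time fall either side of the ad libitum meal

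*Combined protocol and SAP*

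**What the plan says.** **Endpoint.** Section 5.3 defines the primary endpoint in one line: "Changes in appetite as measured by visual analogue scale". Section 11 refers to visual-analogue scores in general. It does not say which item or composite is primary, which direction counts as benefit, or between which times change is taken.

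**Ratings with a described time (section 5.5.3).** The first comes before the drink: "They will be asked to answer a questionnaire regarding your feeling of hunger, satiety and if there is any nausea on a linear scale". The drink follows. Section 5.5.2 gives its time: "It will be given at 9:00 am on an empty stomach prior to the meal". The ad libitum meal is offered at 12:00, and the second rating comes after it: "After the meal they will also be provided with a similar questionnaire to fill in, in order to establish your fullness and satiety level".

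**The Summary.** For the 12:00 part of the visit it says "All subjects will be asked to rate their appetite on a Visual Analogue Scale (VAS) (see appendix B", and then "Upon VAS completion the subjects will be allowed to go home".

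**The form.** Section 6.4.4.4 describes the scales as follows: "Visual analogue scales will be used to assess subjective feelings of malaise, nausea and symptoms of flushing (Appendix B". The readable Appendix B prompts are of that kind, for example "How dizzy do you feel". Two figures in the appendix are not shown in the text available for this review.

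**The schedule.** Table 1 marks visual analogue scales at each of visits 1 to 6, without clock times.

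**The concern.** A change score needs the same item at two stated times, and the plan fixes neither. Several appetite ratings are in play (hunger, satiety, fullness), so the primary result could be chosen after the data are seen.

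The larger issue is where the described ratings sit. The aim is to compare appetite after preloads digested in different parts of the gut. A rating taken after subjects have eaten freely reflects the preload and also the meal they chose to eat. The study hypothesis (section 4) is that the supplement raises satiety and reduces food intake. In a post-meal rating these two effects work against each other. A preload that works as hoped could leave subjects equally full after a smaller lunch, and the primary endpoint would show little. A pre-meal rating that was not taken cannot be recovered afterwards.

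**Working it through.** There is no figure in the plan to reproduce for this endpoint. The only sample-size statement (section 5.5: n = 10, 80% power, alpha 0.05) is for ad libitum energy intake and gives no difference or SD. The check is therefore mainly a reading of the sections side by side.

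**1. Times.** From section 5.5.3, blood is drawn at 09:00 and every 30 minutes to 12:00: 09:00, 09:30, 10:00, 10:30, 11:00, 11:30 and 12:00. That is 7 samples, and 7 × 5 mL = 35 mL, as the section states. With the drink at 09:00, 7 − 1 = 6 samples follow it, over 180 minutes. Appetite ratings described per visit number 2, one before the drink and one after the meal. Ratings described between the drink and the meal number 0.

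**2. Items.** The pre-drink questionnaire names hunger, satiety and nausea. The post-meal one is called similar and names fullness and satiety. Of the three appetite constructs, only satiety is named at both times.

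**3. What the change score contains.** Take any two preloads, A and B, and score satiety so that higher means fuller. Write:

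- D_pre = the A − B difference just before the ad libitum meal (the preload effect);
- ΔI = intake after A minus intake after B;
- g > 0 = the rise in the rating per unit of food eaten.

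To a first approximation, the post-meal difference is D_post = D_pre + g × ΔI. The pre-drink rating precedes treatment, so it cancels in expectation. Under the study hypothesis, if A is the more satiating preload, D_pre > 0 and ΔI < 0, so D_post < D_pre. It reaches zero when g × |ΔI| = D_pre. For a hunger score the signs reverse and the conclusion is the same.

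**4. The plan's own background.** Section 2.1 reports fullness differences from 30 to 180 minutes after a meal. Its Figure 2 legend describes a time course of hunger as change from baseline. Both follow appetite through the interval for which this plan describes no rating.

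**5. Why no power loss is quoted.** The documents give neither the size of the offset nor the SD of VAS differences. A purely hypothetical case shows how little can be said. A paired t test with n = 10 and two-sided 0.05 needs a standardised paired difference of 0.996 for 80% power. Suppose eating less cancels half of the difference. The standardised difference becomes 0.996 × 0.5 / k, where k is the post-meal SD divided by the pre-meal SD:

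| k | Power |
|---|---|
| 0.5 | 80% |
| 0.75 | 47% |
| 1 | 29% |
| 1.25 | 20% |

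The answer depends entirely on assumed inputs, so it is not evidence about this trial.

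**The case against.** The strongest reply is that the plan is silent on timing rather than wrong. Table 1 gives no clock times. Section 11 mentions areas under the curve without saying of what; if VAS is meant, serial ratings would be needed. The Summary lists the meal offer, a blood sample and the appetite rating together at 12:00, so only section 5.5.3 says outright that a rating follows the meal. The narrative is also not in strict clock order: the first questionnaire is mentioned after the 12:00 sample, and only the words leading to the drink place it earlier. This stands. A reader might infer that no appetite rating is taken between 09:00 and 12:00; the documents show only that none is described.

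Second, intake at the same meal is measured and analysed, so similar fullness after less food can be recognised by reading the two results together. This also stands. A null VAS result is hard to read alone, but it would not be uninterpretable.

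Third, a reader might infer from section 6.4.4.4 and the readable prompts that the form has no appetite scale, or that appetite is not measured at all. The documents do not support either. Part of the document, including two appendix figures, is not visible here; the Summary says appetite is rated on that form; and section 5.5.3 describes hunger, satiety and fullness ratings.

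Fourth, making a pre-meal rating primary is a design judgement. That is so, but it is the choice that matches the preload question, and the plan offers no reason for a post-meal primary.

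**Conclusion.** The point holds in this form. The primary endpoint lacks an item, a direction and rating times. The only ratings with a described time are the two either side of the ad libitum meal, with none described in the 180 minutes when the preload acts. A change score built from those two ratings partly measures how much was eaten, which Objective 3 treats as a separate outcome. Under the trial's own hypothesis the mixing tends to shrink the between-meal difference.

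This rests on two assumptions: that section 5.5.3 is followed as written, and that eating more raises the post-meal satiety rating. How much of the difference is lost is unknown, and no power figure should be attached to it.

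The mismatch over Appendix B is a secondary inconsistency between the Summary and section 6.4.4.4. It needs reconciling whichever items the form contains.

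**What to change.** 1. In sections 5.3 and 11, name one appetite item or one composite as the primary score, with its direction, justified on scientific grounds before any data are seen.
2. In section 5.5.3, use identical items at every rating and state the clock times. Add those times to Table 1.
3. Define the primary change as from before the drink to a rating completed before the ad libitum meal is served. This could be a single rating at the 12:00 blood sample or a summary over the existing 30-minute sampling times. In section 11, say whether areas under the curve apply to VAS.
4. Keep the post-meal rating as supportive, and report it together with intake.
5. Reconcile the Summary, section 6.4.4.4 and Appendix B. If the unseen figures already hold appetite scales, only the wording and cross-references need correcting.

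**Cost.** Short text edits, possibly a revised form, and the ethics-approved amendment that section 13.1 requires. If no pre-meal rating is currently taken, the minimum is 1 extra rating × 6 visits × 10 subjects = 60. Rating at all six post-drink samples would be 6 × 6 × 10 = 360. Either fits times when staff are already drawing blood.

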6.5 Data collection and storage

All screening data will be entered on a Screening Excel Database. Only individuals who match the recruitment criteria should be entered on this database. The following information should be inserted into the Screening Database.

Subjects Initials	Volunteer Code Number	DOB (dd/mm /yy)	Gender (M/F)	Ht (m)	Wt (Kg)	BMI (kg/m ²)	Pulse beat/min	Blood Pressure (mm Hg)	Waist Circ. (cm)

GLP-1	PYY	Glucose	AST	ALT				

Subjects Initials – A four-digit code, the first two letters of their first and surname (e.g. HERO for [name]) assigned at the screening stage. This should be also be used on the Screening CRF. Volunteer code number – A Volunteer Number should only be assigned to volunteers who are suitable for the study. Only suitable volunteers should be included in the Screening Database. Volunteer codes numbers assigned following successful screening will be used throughout the study.

6.6 Sample transport

Samples will be transported from St. Vincent's University Hospital to the Conway Institute, University College Dublin where sample analysis will take place. Samples will be stored at this location in accordance with the above instructions

6.6.1 Blood samples processing

Serum will be separated immediately by centrifugation at 4°C and then stored at - 20°C freezer until analysis. GLP-1 and PYY assays will be performed on each sample.

7 Adverse event program

7.1 Subject premature Withdrawl

If a study volunteer fails to complete the study protocol it will be documented in the individual case report form. The reason for failure to complete the study will be included in the CRF. Study Subjects may be withdrawn for the following reasons

- Adverse Event(s) (AEs)
- Abnormal laboratory value(s)
- Protocol violation
- Subject withdrew consent
- Lost to follow-up
- Death

All patients who withdraw early from the study will have their GP informed in writing that their participation in the study is complete. In the event of adverse event, GP's will be informed and arrangements will be made for subjects who have a requirement for ongoing medical follow-up as a consequence of an adverse event.

7.1.1 Adverse Events

An adverse event (AE) is defined as "any untoward medical occurrence in a patient or clinical investigation subject administered a pharmaceutical product and which does not necessarily have to have a causal relationship with this treatment". The principal investigator (PI) will be informed of any adverse events affecting participants within 24 hours of the research investigator becoming aware of them. The suitability of the participant to continue

with the study will be determined by the PI. All adverse events will be recorded in the CRF and the adverse events log contained within the site file. A data safety monitoring committee will be establish consisting of a senior physicians. All events will be reported within 7 working days and decisions to progress or stop the study will be made in conjunction with the Ethics committee.

7.1.2 Serious Adverse Events

A serious adverse event (SAE) or reaction is defined as any untoward medical occurrence that:

- Results in death
- Is life-threatening
- Requires inpatient hospitalisation or prolongation of existing hospitalisation
- Results in persistent or significant disability/incapacity, or
- Is a congenital anomaly/birth defect.

The term "life-threatening" in the definition of "serious" refers to an event in which the patient was at risk of death at the time of the event; it does not refer to an event which hypothetically might have caused death if it were more severe. The principal investigator (PI) will be informed of any adverse events affecting participants within 24 hours of the research investigator becoming aware of them. The suitability of the participant to continue with the study will be determined by the PI. All adverse events will be recorded in the CRF and the adverse events log contained within the site file. A data safety monitoring committee will be establish consisting of a senior physicians. All events will be reported within 7 working days and decisions to progress or stop the study will be made in conjunction with the Ethics committee.

8 Insurance and Indemnity

Clinical staff will be covered under the institutional Clinical Indemnity Scheme (CIS).

9 Reimbursement

All participants will be reimbursed for travel and parking expenses incurred while participating. Volunteers will not be paid to participate in this study.

10 Data management

Data will be collected and stored in both paper and electronic format. Paper data will be filed and stored in a locked office at the Clinical Research Centre, St Vincents University Hospital. Electronic data will be password encrypted. All data will be handled in line with data protection legislation.

11 Statistical analysis

Data will be analysed using GraphPad Prism (version 6.0) for Windows, GraphPad software (San Diego, CA, USA) and SPSS® (version 20.0) software (SPSS, Chicago, IL, USA). Central tendencies for patient and control group demographics, anthropometric data, caloric intake, VAS scores, QoL scores and macronutrient intake will be calculated and expressed using arithmetic mean \pm standard error of the mean or median (range), as appropriate. Differences in continuous variables between surgical and control groups will be calculated using the Student's *t* test or Mann-Whitney U test for parametric or non-parametric data, respectively. Correlative analyses will be performed using the Spearman Rho rank correlation to assess the relationship between *ad libitum* caloric intake and macronutrient intake with peri-operative weight loss and anthropometric data. Univariate analysis of factors associated with perioperative and post-surgical weight loss will be performed using Student's *t* test or one-way ANOVA for categorical variables or simple logistic regression for continuous variables. For the multivariate analysis, independent variables which were significant on univariate analysis, including standard demographic, oncologic and operative parameters as well as food intake and food preference, will be entered into a multiple logistic regression model with a forward stepwise selection procedure to assess their impact on perioperative and post-surgical weight loss. All statistical analyses will be two-tailed with the threshold of significance set at $P < 0.05$. Caloric intake and visual-analogue scores within groups will be compared by the Wilcoxon signed rank, matched-pairs test. Areas under the curve and plasma hormone levels will be compared by Wilcoxon rank-sum analysis.

12 Duration of Project

The estimated duration of the study will be 12 months. Screening and recruitment will begin in May 2017. Completion of the study is planned for May 2018.

13 Administrative considerations

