The goal of the present study is to investigate the physiological effect of natural macronutrients when delivered exogenously to the proximal and distal small bowel. This will mimic some aspects of the physiological changes after Roux-en-Y gastric bypass. The oral administration of macronutrients in a protective capsule will enable us to deliver them to the proximal or the distal part of the small intestine depending on the chemical and physical properties of the capsules. Our study will provide important information on the physiological role of protein, fat, and carbohydrate content of the ingested food on specific gut hormone secretion and their effects on satiety

3 Potential side effects and risks

Blood sampling can cause mild pain and/or bruising. A doctor or a trained phlebotomist will insert this with experience in obtaining blood samples to minimise the discomfort caused. We do not expect any severe side effects

4 Study hypothesis

The delivery of high protein supplement to the proximal and distal gut will increase the release of anorexigenic gut hormones that have powerful satiety effect and will reduce food intake.

5 Study Objectives and Design

5.1 Primary Aim:

To identify the physiological satiety gut hormone response and the satiety response of subjects when macronutrients are digested in the distal rather than proximal small bowel.

5.1.1 Objective 1:

To quantify the physiological gut hormones response of differential macronutrient delivery to the proximal and distal small bowel.

5.1.2 Objective 2:

To quantify the physiological satiety response of differential macronutrient delivery to the proximal and distal small bowel.

5.1.3 Objective 3:

To quantify the amount of food consumed after a preload of differential macronutrient delivery to the proximal and distal small bowel.

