5.2 Study design

This is a randomized six-way crossover study. The study will include 10 healthy volunteers with each subject being studied on six separate occasions at weekly intervals (Figure 3).

[figure not shown]

Figure 3: Schematic of Study Design

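### Section 11 analyses a surgical weight-loss study: it never names the distal-versus-proximal contrast and gives within-subject hormone data an independent-samples test

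*Combined protocol and SAP*

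**What the plan says.** The design is a single-group crossover: "This is a randomized six-way crossover study" (Section 5.2), with ten volunteers seen six times at weekly intervals. The Summary lists the six drinks, which are three macronutrient mixes each in a gastric-release and a distal-release capsule. The primary aim (Section 5.1) concerns the response "when macronutrients are digested in the distal rather than proximal small bowel". The primary endpoint (Section 5.3) is "Changes in appetite as measured by visual analogue scale", and gut hormone concentrations are secondary (Section 5.4). The hypothesis in Section 4 is narrower and concerns protein: "The delivery of high protein supplement to the proximal and distal gut will increase the release of anorexigenic gut hormones".

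Section 11 sets out these comparisons:

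- Group comparison: "Differences in continuous variables between surgical and control groups will be calculated using the" Student's t or Mann-Whitney test.
- Correlations of intake with peri-operative weight loss and anthropometry, then univariate and forward stepwise logistic models with oncologic and operative covariates, "to assess their impact on perioperative and post-surgical weight loss".
- Intake and VAS: "Caloric intake and visual-analogue scores within groups will be compared by the Wilcoxon signed rank, matched-pairs test".
- Hormones: "Areas under the curve and plasma hormone levels will be compared by Wilcoxon rank-sum analysis".

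It also plans descriptive summaries and a two-sided 5% threshold.

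**The concern.** Most of Section 11 cannot be carried out. The trial has no surgical or control group, no operative or oncologic variables and no weight-loss outcome, and Table 1 lists no quality-of-life measure. Section 11 does not mention release site, visit or sequence.

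Two of its comparison rules can be applied to the trial's endpoints, and neither answers the aim.

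- **Hormones and AUC.** The rank-sum test treats the two drinks' values as coming from different people. It throws away the pairing that the crossover was chosen to provide, so a real distal-proximal difference can be missed.
- **VAS and intake.** The signed-rank test respects the pairing. However, the plan does not say which drinks are paired, whether the macronutrients are pooled, how visit effects or multiple tests are handled, or what estimate and interval will be reported. Those choices would be made with the data in hand.

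**Working it through.** **Inputs from the documents.** n = 10 subjects, six drinks (3 macronutrients × 2 release sites), two-sided alpha 0.05, 80% power (Sections 5.2, 5.5 and 11). Section 5.5 bases n = 10 on ad libitum energy intake but gives no difference, SD, correlation or test, so it cannot be reproduced.

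**Assumptions.** Normal data. Within-subject correlation rho is not given, so it is varied. The effect is back-solved from n = 10 and 80% power.

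**Step 1: implied effect.** For a paired t test, power = P(|t with 9 df, ncp = dz·√10| > critical value), where dz is the mean difference divided by the SD of the differences. Solving for 0.80 gives dz = 0.996.

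**Step 2: rank-sum against signed-rank.** Exact tests at n = 10: signed-rank rejects at W ≤ 8 (size 0.0488); rank-sum, 10 v 10, rejects at U ≤ 23 (size 0.0433 if samples were independent). Results are from 100,000 simulated trials per setting at dz = 0.996:

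| rho | rank-sum power | rank-sum type I error | signed-rank power |
|---|---|---|---|
| 0.3 | 0.679 | 0.0194 | 0.78 |
| 0.5 | 0.521 | 0.0089 | 0.78 |
| 0.7 | 0.280 | 0.0022 | 0.78 |

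At rho = 0 the two tests perform alike (rank-sum power 0.80).

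**Step 3: unnamed pairs for VAS and intake.** Six drinks give 6·5/2 = 15 possible pairs, three of which are matched distal-proximal pairs. Testing those three unadjusted by signed-rank gives 1 − (1 − 0.0488)³ = 0.139 (simulated 0.138).

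**Step 4: what a named contrast would deliver.** Take each subject's mean of the three distal-minus-proximal differences and test it on 9 df. With equal site effects and no subject-by-site variation, ncp = dz·√30, where dz is per pair.

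- Power is 80% at dz = 0.575 (ncp 3.15), against about 1.0 for a single pair.
- At dz = 0.53 (ncp 2.90), power is 0.734 on 9 df. It is 0.809 on 40 df, but that test is valid only without subject-by-site variation.
- If only protein has an effect (dz 0.996), the averaged effect is 0.996/3 = 0.332, ncp = 1.82 and power is 0.369 on 9 df.

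**Step 5: why subject-by-site variation matters.** Let k be the subject-by-site variance divided by the residual variance. With dz scaled to the total SD of a pair difference, ncp = dz·√[10(1 + k)/(k + 1/3)].

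| k | 9-df power at dz 0.53 | type I error, 40-df test without the term |
|---|---|---|
| 0 | 0.73 | 0.051 |
| 0.25 | 0.59 | 0.101 |
| 0.5 | 0.52 | 0.141 |
| 1.0 | 0.45 | 0.196 |

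The 9-df test keeps its type I error at 0.048 to 0.052 throughout.

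**The case against.** The primary endpoint and intake already have a paired test, so the wrong-test point is confined to hormones and AUC. The rank-sum error there is conservative and costs power without adding false positives. Both statements are correct, and the conclusion is limited accordingly.

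The power gradient depends on holding dz fixed, which shrinks the raw effect as rho rises. With the raw shift fixed at 1.0 SD, rank-sum power is roughly flat at 51–56% for rho from 0 to 0.8, while signed-rank rises from about 49% to 99%. At dz = 1.5, rank-sum power is 97%, 91% and 73% at rho 0.3, 0.5 and 0.7. The documents give no hormone effect size, so the loss could be small if the effect is very large. It is still a loss at any positive rho shown.

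Some of Section 11 does carry over: the descriptive summaries, the significance threshold and the correlation of intake with anthropometry. None of these is a comparison of distal with proximal release. The absence of quality of life from Table 1 is weak evidence alone, since that table also omits the ad libitum meal. The point does not depend on it.

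The 14% figure applies only if any one of three significant pairs would be read as success, which the plan neither says nor excludes.

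The strongest objection concerns the remedy. Section 4 is about protein, and if only protein works the pooled contrast has 37% power, against about 78% for a signed-rank test on the protein pair alone. This stands as a reason for the investigators to choose the target deliberately. It does not support leaving the contrast unnamed. The particular mixed model and the Holm step are likewise one reasonable choice among several.

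**Conclusion.** The concern holds and must be fixed before analysis. Followed as written, Section 11 compares groups that do not exist, models an outcome the trial does not have, and applies an independent-samples test to repeated measurements on the same ten people. No other section supplies the missing distal-minus-proximal analysis. This textual finding depends on no assumed number.

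The size of the hormone problem does depend on assumptions. With normal data and dz = 0.996, power falls from about 78% to between 68% and 28% for rho between 0.3 and 0.7. For VAS and intake the harm is undirected choice among pairs, with a family-wise error of about 14% if the three matched pairs are each tested at 5%, and no planned estimate or interval for the primary aim.

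**What to change.** Essential changes:

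- Delete the surgical, control, peri-operative, oncologic, quality-of-life and stepwise logistic text.
- Name one within-subject release-site contrast as primary, on one stated VAS appetite item and time point, reported as a difference with a 95% confidence interval.
- Replace the rank-sum test for hormones and AUC with a within-subject analysis.

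A suitable model for VAS, intake and hormones is a linear mixed model. Fixed effects are release site, macronutrient, their interaction and visit, plus the same-day baseline where one exists. Random effects are subject and subject-by-site. With complete data and balanced visit order, testing each subject's mean distal-minus-proximal difference on 9 df is equivalent. Section 5.5.3 does not describe a balanced order, so the visit term should stay unless balance is confirmed. Report the three macronutrient-specific contrasts as secondary with Holm adjustment. If the protein hypothesis in Section 4 is the real target, make the protein distal-minus-proximal contrast primary instead.

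The cost is a rewrite of Section 11 and a line in Section 5.3. No additional participants are needed, and SPSS, already named, fits the model. The team must first settle the VAS item. The readable Appendix B items concern anxiety, stress, nausea, dizziness and flushing; figures there are not visible to this review, so the team should confirm that an appetite item is on the form.

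The trade-offs are in steps 4 and 5: the pooled contrast loses power if subjects differ in their site response or if only one macronutrient has an effect, and the Holm-adjusted contrasts face a stricter threshold. At Holm's first step (0.05/3), a paired t test on a single pair with dz = 0.996 has about 60% power.
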